During the study, two FDA-cleared spinal cord stimulator leads (Infinion 16; Boston Scientific; PMA P030017) will be placed in the cervical epidural space of ten upper-limb amputees and steered laterally towards the dorsal spinal roots under fluoroscopic guidance. This approach is essentially identical to the FDA-cleared procedure in which these devices are placed in the epidural space for treatment of intractable low back and leg pain. In that procedure, it is common clinical practice to place 2-3 leads temporarily in the epidural space through a percutaneous approach and perform a multi-day trial to determine if the patient experiences any pain reduction from spinal cord stimulation. Following the trial, the percutaneous leads are

typically removed by gently pulling on them, and the patient is referred to a neurosurgeon for permanent surgical implantation. Similarly, in this study, the device will be tunneled percutaneously through the skin and secured in place with tape. Using the stylet included with the spinal cord stimulator leads, the devices will be steered laterally under fluoroscopic guidance to target the dorsal spinal nerves. During lab experiments, the leads will be connected to an external stimulator. In clinical practice, the devices are typically left in the epidural space for one week or more, in order to determine whether patients experience any benefits from stimulation, including those with delayed onset. In this study, the devices will remain in the epidural space for less than 30 days and will be removed by gently pulling on the external portion. This extended testing period will have multiple benefits, as it will allow us: 1.) to quantify changes in the response to stimulation over time, 2.) to thoroughly explore the sensations that occur during electrical stimulation, 3.) to explore the effects of those sensations on functional use of a prosthetic limb, and 4.) to observe any delayed effects of stimulation on phantom limb pain. Throughout the study, we will perform a series of psychophysical evaluations to characterize the sensory percepts evoked by epidural stimulation, along with functional evaluations of the effects of stimulation on the ability to control a prosthetic limb. In addition, we will perform a survey to characterize changes in phantom limb sensation and pain that occur during stimulation.

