Periodically throughout the experimental sessions, we will ask each subject to rate their current phantom limb pain from 0-10 on a visual analog scale, and to describe any subjective effects of stimulation on their phantom limb sensations and pain. We will also administer the pain portion of the Trinity Amputation and Prosthesis Experience Scales [26] before device placement, at least once during the <30 day testing portion of the study, and again within a month after device removal. We may also administer the McGill Pain Questionnaire before device placement, during testing, or within a month after device removal [27]. Other similar questions may be developed to best capture the effect of stimulation.

- Closed-loop Control of a Prosthesis:

During some sessions, participants will be asked to control a prosthesis with and without sensory stimulation. The prosthesis may be their own device, a device provided by the lab, or a

virtual reality hand. When physical devices are used, they will be instrumented with sensors that measure force and joint angle, and signals from those sensors will be used to modulate stimulation. Any sensors placed on the participants prosthesis will be easily attached and removed from the device (e.g. small electrogoniometers, thin strain gauges), and will be removed at the end of the session. EMG signals will be recorded from the muscles in the residual limb using surface electrodes, and participants will be asked to perform tasks that test their ability to utilize sensory stimulation such as manipulating blocks, opening a jar, or identifying the stiffness and size of various objects.

- Initial Stimulation Parameters:

When stimulation commences on an electrode that has not been previously used, stimulation parameters will be set conservatively in order to minimize the chance for eliciting an undesired response. Pulse train duration and then pulse frequency will be increased as these are the least likely to modify electrical recruitment of neurons in the vicinity of electrodes, yet may increase the detectability of the stimulus due to synaptic integration at downstream neural pathways. Pulse amplitude will be the last parameter increased as this is expected to have the most significant effect on neural recruitment and detectability.

- Electrode Impedance:

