## STUDY AIMS

1. The proposed study is a pilot study to examine the perceived sensations evoked in upper-limb amputees during electrical stimulation of the spinal nerves, the effect of sensory feedback on control of a prosthetic limb, and the effect of stimulation on phantom limb pain. Results of this study will provide the foundation for future development of a neuroprosthesis to restore sensory function to individuals with upper-limb amputation, thereby increasing the functionality of prosthetic limbs and improving quality of life.

Specific Aim 1: Characterize the sensations evoked by cervical epidural spinal nerve stimulation in upper-limb amputees, and quantify changes in those sensations over time.

Specific Aim 1a: Quantify the threshold (minimum charge and pulse rate) stimulus required to evoke sensory percepts and neurophysiological responses (e.g. reflexive EMG responses, somatosensory evoked potentials) during epidural spinal nerve stimulation, and monitor changes in those percepts and responses over time. These results will provide insight into the design requirements for future implantable epidural spinal nerve stimulators, as well as a point of comparison among subjects and with other studies in the scientific literature. Additionally, the stability of the responses will provide

insight into the feasibility of long-term use of the device.

Specific Aim 1b: Evaluate the relationship between stimulation parameters (e.g. pulse width, pulse amplitude, stimulus location, etc) and the modality and naturalness of perceived sensations. Based on results from the literature and anecdotal experience of co-investigators on this study, we expect that cervical spinal nerve stimulation can evoke paresthesias referred to the amputated limb, but our goal is to produce meaningful (non-paresthetic) sensations. As we expect the stimulation parameters to have significant effects on the evoked sensations, we will perform standardized psychophysical examinations to determine the relationship between stimulation parameters and the perceived sensations. These tests will be repeated at multiple points throughout the study to observe any changes that occur over multiple days of use.

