Specific Aim 3: Characterize changes in control of a prosthetic hand in the presence of sensory feedback. The long-term goal of this line of research is to provide sensory feedback that can be used in the control of a prosthetic hand. In this study, we will test the subject's ability to use a myoelectric prosthetic hand with and without sensory feedback provided by electrical stimulation of the spinal roots. Using either a virtual prosthetic limb or an instrumented prosthesis, stimulation of the spinal roots will be modulated based on signals recorded from the limb such as pressure at the finger tips or joint angles. In both the presence and absence of stimulation, subjects will be asked to perform tasks such as manipulating blocks, opening a jar, or identifying the stiffness and size of various objects.

2. **\* Describe the relevant prior experience and gaps in current knowledge including preliminary data. Provide for the scientific or scholarly background for, rationale for, and significance of the research based on existing literature and how it will add to existing knowledge:**

It is estimated that by 2020, over 2.2 million people in the United States will be living with limb loss [1]. Upper extremity amputations are predominantly traumatic injuries occurring in relatively young and active individuals, and can lead to significant decreases in function and impairment in activities of daily life [2]. Additionally, phantom limb pain after amputation can lead to further impairment and withdrawal from social activities [3]. While there have been important improvements in prosthetic limb technology over the last decade, the control of these limbs remains non-intuitive and the lack of sensory feedback results in the requirement of significant visual attention during use of these devices. Further, treatment of phantom limb pain with pharmaceuticals is often ineffective and can result in significant side effects [4].

Restoration of sensory function is a crucial step in the further development of truly integrated prosthetic devices. Without provisions for sensory feedback, even the most advanced limbs, even those under 'neural control' will remain as numb, extracorporeal 'tools', rather than fully integrated functional limbs. In the upper extremity, body powered prostheses have remained the preferred choice for many amputees, in part

because users receive proprioceptive feedback from the control cable [13].

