Specific Aim 3: Characterize changes in control of a prosthetic hand in the presence of sensory feedback. The long-term goal of this line of research is to provide sensory feedback that can be used in the control of a prosthetic hand. In this study, we will test the subject's ability to use a myoelectric prosthetic hand with and without sensory feedback provided by electrical stimulation of the spinal roots. Using either a virtual prosthetic limb or an instrumented prosthesis, stimulation of the spinal roots will be modulated based on signals recorded from the limb such as pressure at the finger tips or joint angles. In both the presence and absence of stimulation, subjects will be asked to perform tasks such as manipulating blocks, opening a jar, or identifying the stiffness and size of various objects.

4. **\* Describe the relevant prior experience and gaps in current knowledge including preliminary data. Provide for the scientific or scholarly background for, rationale for, and significance of the research based on existing literature and how it will add to existing knowledge:**

It is estimated that by 2020, over 2.2 million people in the United States will be living with limb loss [1]. Upper extremity amputations are predominantly traumatic injuries occurring in relatively young and active individuals, and can lead to significant decreases in function and impairment in activities of daily life [2]. Additionally, phantom limb pain after amputation can lead to further impairment and withdrawal from social activities [3]. While there have been important improvements in prosthetic limb technology over the last decade, the control of these limbs remains non-intuitive and the lack of sensory feedback results in the requirement of significant visual attention during use of these devices. Further, treatment of phantom limb pain with pharmaceuticals is often ineffective and can result in significant side effects [4].

Restoration of sensory function is a crucial step in the further development of truly integrated prosthetic devices. Without provisions for sensory feedback, even the most advanced limbs, even those under 'neural control' will remain as numb, extracorporeal 'tools', rather than fully integrated functional limbs. In the upper extremity, body powered prostheses have remained the preferred choice for many amputees, in part because users receive proprioceptive feedback from the control cable [13].

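### Aim 3 compares prosthesis control only with stimulation on versus off, so block and jar results give the total effect of stimulation and cannot show that subjects used the sensor information

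*Combined protocol and SAP*

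**What the plan says.** The protocol item Closed-loop Control of a Prosthesis states that, in some sessions, "participants will be asked to control a prosthesis with and without sensory stimulation". For physical devices fitted with force and joint-angle sensors, "signals from those sensors will be used to modulate stimulation". The purpose of the tasks is given in the same item: "tasks that test their ability to utilize sensory stimulation such as manipulating blocks, opening a jar, or identifying the stiffness and size of various objects".

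Specific Aim 3, which appears twice under Study Aims, sets the same contrast: "In both the presence and absence of stimulation, subjects will be asked to perform tasks such as manipulating blocks, opening a jar". It describes the device under test as a "myoelectric prosthetic hand with and without sensory feedback provided by electrical stimulation of the spinal roots". The opening of Study Aims lists among the study's purposes "the effect of sensory feedback on control of a prosthetic limb".

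Neither place describes constant, replayed, shuffled or otherwise sensor-uncoupled stimulation during prosthesis tasks. Neither describes masking, or a random or counterbalanced order of on and off trials. The varied pulse patterns listed under Psychophysical testing, and the mechanical and electrical stimuli applied to the limbs, serve to characterise sensations. They are not controls for Aim 3.

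**The concern.** The on and off conditions differ in at least two respects. In the on condition the stimulation carries information about force and joint angle, and the subject feels a sensation referred to the missing limb. The subject can tell which condition is running simply by feeling it. Alertness, effort or expectation could therefore change how well someone moves blocks or opens a jar, without any use of the sensor signal.

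The protocol itself raises two further routes. The background expects stimulation to reduce phantom limb pain, and less pain could change performance. Aim 1a lists reflexive EMG responses among the responses to be measured, while residual-limb EMG is recorded during these tasks for a myoelectric hand. The background argues that stimulation at this target will not contaminate the myoelectric signal, but an on/off comparison does not test that.

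What is at stake is attribution. A gain on the block and jar tasks would support the statement that switching stimulation on changes performance. It would not support the statement that the feedback was used. Once a subject's leads are out, which the protocol requires by day 29, the missing condition cannot be collected for that placement.

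**Working it through.** **Inputs.** The contrast is on versus off (Closed-loop Control of a Prosthesis; Specific Aim 3). The sample size is ten: leads "will be placed in the cervical epidural space of ten upper-limb amputees" (Brief Description). The Power Analysis section gives no alpha, effect size, SD or test, so there is no figure in the plan to reproduce.

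**Step 1: what each contrast identifies.** For a block or jar score, let I be the effect of using the sensor information and N the effect of feeling any stimulation.

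- On − off = I + N.

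This is one difference with two unknowns. More subjects estimate the sum more precisely but do not split it. Randomising the order of on and off trials removes practice and fatigue trends, but not N.

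**Step 2: what an uncoupled condition adds.** Let U be perceptible stimulation not linked to the current sensor signals, and let M be any effect of its mismatch with the task (negative if it misleads). If N is equal in the two stimulated conditions:

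- U − off = N + M
- On − U = (I + N) − (N + M) = I − M

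If M = 0, on − U isolates I. If the uncoupled trains mislead (M < 0), on − U exceeds I. For example, I = 0 and M = −0.3 SD give on − U = +0.3 SD with no use of feedback. So on versus U should not be reported alone. U versus off shows whether the uncoupled stimulation helps or harms on balance, although it still does not separate N from M.

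**Step 3: illustration of size, under assumptions.** Assume a two-sided 5% paired t-test, ten complete pairs and I = 0. The critical value is t(0.975, 9 df) = 2.262. With d = N divided by the SD of the within-subject difference, the noncentrality is d√10. The probability of a significant result in favour of stimulation is P(T > 2.262), where T is noncentral t on 9 df:

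| Assumed d | d√10 | Probability favouring stimulation |
|---|---|---|
| 0 | 0 | 0.025 |
| 0.2 | 0.632 | 0.082 |
| 0.3 | 0.949 | 0.134 |
| 0.5 | 1.581 | 0.293 |

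Counting both tails, the rates at 0.3 and 0.5 SD are 0.136 and 0.293 with ten pairs, and 0.114 and 0.232 with eight. If N is equal in the two stimulated conditions and M = 0, a test of on versus U has the nominal two-sided rate of 0.05.

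**The case against.** The strongest reply is that on versus off is the right contrast for what Aim 3 asks. The aim is to characterise changes in control when feedback is present. The study is a ten-subject pilot with no stated hypothesis test or success criterion, and a mechanistic control could reasonably wait until an on/off effect has been seen. This limits the weight of the point. It does not remove it, because the protocol also says the tasks test the ability to use the stimulation, and on/off cannot show that for blocks and jars.

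A reader might infer that the protocol already claims this study will show usable feedback. It does not: the sentence about feedback that can be used in controlling a hand states a long-term goal of the research line.

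A reader might also infer that Aim 3 cannot show any use of information. That goes too far. Identifying size or stiffness requires information about the object, and an uninformative sensation does not supply the answer, although general attention could still contribute. The gap concerns the manipulation tasks, which are themselves given as examples.

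The objection to the remedy also stands in part. Replayed trains can signal contact at the wrong moment. A subject who sees the object may notice the mismatch, so masking may fail and expectation may differ between the two stimulated conditions. These limits need to be stated with the results.

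**Conclusion.** The point holds within a narrow scope. On the block and jar tasks, the planned comparison estimates the total effect of switching on perceptible, unmasked stimulation. It cannot attribute a change to the sensor information at any sample size. That conclusion follows from the two conditions described and needs no numerical assumption.

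The 8%, 13% and 29% figures do need assumptions: the paired t-test, ten complete pairs and shifts of 0.2, 0.3 and 0.5 SD. They show what a non-specific effect of that size would do. They are not evidence that such an effect exists, and the documents supply none of those values.

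The change is worth making because it fits within planned sessions and concerns something the protocol says it wants to test. It is not a reason to regard the on/off comparison as invalid. That comparison remains the correct estimate of the overall effect.

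**What to change.** In the manipulation tasks, add a third condition: stimulation uncoupled from the current sensor signals, on the same contacts, with a similar amplitude range and duration. Constant stimulation or trains replayed from another trial would both serve. Interleave the three conditions in random order, and do not tell the subject which of the two stimulated conditions is running.

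Report all three contrasts:

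- Sensor-linked versus uncoupled, as the contrast for use of feedback.
- Uncoupled versus off, to show whether uncoupled stimulation helps or harms by itself.
- Sensor-linked versus off, as the total effect.

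State that mismatched trains may mislead and that masking may be incomplete. Ask subjects to guess the condition, and report the guesses.

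Where the third condition is not run, limit the block and jar conclusion to the total effect of stimulation, and rest any claim that feedback was used on the identification tasks. This fallback costs nothing.

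The cost of the third condition is fewer repeats per condition or longer task blocks, plus a small software change. The protocol already allows as many as five sessions weekly of up to eight hours each, so no extra subjects, staff or procedures are needed.

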Periodically during the experimental session, we may measure the impedance of the SCS leads as a means to ensure that the device is functioning properly. This functionality is included in the Boston Scientific External Trial Stimulator and the Ripple stimulator.

- Removal of SCS Leads:

After completion of testing and no later than 29 days after device placement, the SCS leads will be removed at UPMC Mercy. To remove these devices, the subject will be positioned prone on an examination table, and using sterile technique, the lead will be gently pulled until it is removed. Visual inspection of the leads will confirm that they are intact and that no portion of the device remains under the skin. The skin will be cleaned with hibiclens and dried with sterile 4x4s, and a sterile bandage will be placed on the site. A follow-up telephone call will be made to the patient within 48 hours of their discharge to make sure they are asymptomatic. After this follow-up call no further follow up will be required after device removal unless the subject had significant reduction in pain during stimulation. In that case, the subject will be referred to a neurosurgeon for consultation on permanent implantation of a SCS device.

- After device removal, subjects will be instructed on care of the wound and provided with a list of symptoms that may occur (e.g. headache as a result of CSF leak, elevated temperature as a

result of infection). Within two days after removal, a member of the study team will contact the subject to check for any relevant symptoms. Within one month after removal, a member of the study team will contact the subject to document any long-lasting effects of stimulation on phantom limb sensations and pain.

-Possible Second Lead placement:

If excessive lead migration or premature lead breakage occurs during the study, it may be necessary to remove the leads. In this case, the subject may be offered the opportunity to undergo a second lead placement procedure, followed by an additional 29 days of testing. At a study physician's discretion, we may repeat pre-operative testing (e.g. bloodwork) before device replacement. All testing procedures will be repeated as described above and the devices will be removed within 29 days after device replacement. The replacement procedure can happen a maximum of one time per subject.

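### Does the lead-removal text cancel the phantom limb assessment planned within a month of removal?

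*Combined protocol and SAP*

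**What the plan says.** All the relevant text is in the protocol, under Research Activities and Study Aims.

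- **Removal of SCS Leads, end of the bullet.** "A follow-up telephone call will be made to the patient within 48 hours of their discharge to make sure they are asymptomatic". Then: "After this follow-up call no further follow up will be required after device removal unless the subject had significant reduction in pain during stimulation". The exception is completed by: "In that case, the subject will be referred to a neurosurgeon for consultation on permanent implantation of a SCS device".
- **The next bullet, on care after removal.** It covers wound instructions and a symptom contact within two days, and continues: "Within one month after removal, a member of the study team will contact the subject to document any long-lasting effects of stimulation". The effects it names are those on phantom limb sensations and pain, and no condition is attached.
- **Effects on Phantom Limb Sensation and Pain.** The TAPES pain portion is given before placement, at least once during testing, "and again within a month after device removal". The McGill questionnaire is optional. For in-session ratings, "we will ask each subject to rate their current phantom limb pain".
- **Specific Aims 2a and 2b** (printed twice in identical terms). Subjects with a history of phantom limb pain update their limb perception and pain level during sessions and within a month of removal. Aim 2 is declared secondary to Aim 1, and people without phantom limb pain may enrol.
- **Possible Second Lead placement.** "All testing procedures will be repeated as described above and the devices will be removed within 29 days after device replacement", and "The replacement procedure can happen a maximum of one time per subject".

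**The concern.** The first of these statements ends follow-up at the 48-hour call, apart from one exception that leads only to a referral. The others plan an assessment weeks later. Taken word for word they do not sit together, because the restricting sentence does not say that it concerns clinical follow-up only.

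Aims 2a and 2b ask what happens to phantom sensation and pain during stimulation and shortly afterwards. The contact at about 48 hours only checks symptoms, so the assessment within a month is the sole source for the period after removal. If it were dropped, that part of Aim 2 would have no data. If the exception were taken to mean that only subjects whose pain fell are followed, the remaining data would be selected on in-study response and would tend to flatter any lasting effect. With ten subjects, each missed contact removes 1/10 = 10% of the post-removal data.

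Two smaller doubts go with it. Aim 2a ties the sensation update to a history of pain, which on its own would pass over someone with phantom sensation but no such history. And if leads are replaced, the month could run from either of two removals.

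**Working it through.** The plan gives no figure to reproduce here, so the check is a comparison of texts and a count.

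**1. Context of the restricting sentence.** It ends a bullet on positioning, sterile technique, inspection of the leads and dressing. The call before it is a symptom check after discharge. The sentence after it is a surgical referral. No research measurement appears anywhere in that bullet. The following bullet mentions a symptom contact within two days and then goes on to the one-month contact about phantom sensations and pain. One bullet closes the clinical procedure and the next sets out what the study team does.

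**2. Force of the words.** Saying that nothing more is required does not forbid a contact that another sentence says will be made. The two can both be carried out.

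**3. Count of provisions for an assessment within a month of removal** (the repeated aims counted once, the optional McGill questionnaire left out):

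| Provision | Condition |
|---|---|
| TAPES pain portion | none |
| Study-team contact, bullet after removal | none |
| Aim 2a, limb perception | history of phantom limb pain |
| Aim 2b, pain level | history of phantom limb pain |

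Total 1 + 1 + 1 + 1 = 4, of which 2 are unconditional, 2 depend on pain history and 0 depend on response.

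**4. Subjects with a planned assessment, out of the ten in the Brief Description.**

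- Restricting sentence taken alone: 0. Its exception adds a referral and no research measurement, so it does not create a responders-only sample either.
- TAPES and study-team contact: 10.
- Aims 2a and 2b taken alone: k, the number with a history of phantom limb pain. The documents do not give k, so it can be anything from 0 to 10.

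Following every provision together gives 10, because the two unconditional ones already cover everyone.

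**5. Aim 2a.** The difference 10 − k counts everyone without a pain history, including people with no phantom sensation at all, so it is only an upper bound on those Aim 2a might pass over. The unconditional study-team contact covers sensations as well as pain, so those subjects are reached anyway.

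**6. Second placement.** One replacement is allowed, so there are at most 1 + 1 = 2 removals per subject. Testing is to be repeated as before, and a window of one month after removal can apply to each removal. Counting only from the final one would be a preference, and it might lose a contact due after the first, since the documents give no interval between first removal and replacement.

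**The case for a change.** The strongest case for a change is that a protocol should not leave staff to infer which of two neighbouring statements governs. The trigger in the restricting sentence, a fall in pain during stimulation, is also a change that Aim 2b studies. It is not a complication of removal, so the sentence is not cleanly marked as a safety provision. The data at stake have no other source, the sample is ten, and one clause would cure the problem at almost no cost.

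The textual part of this stands: the sentence is unqualified and could have been better worded. The inference from it does not. Pain reduction appears there only as the ground for a surgical referral, and the mandatory one-month contact begins in the next bullet. Confusion among staff over whom to contact is possible, but nothing in the documents points to it. A clarifying clause would do no harm, yet it would add no contact, no measurement and no analysis to those already planned. Recording the day on which each subject was reached is ordinary practice that analysts would follow without an amendment.

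**Conclusion.** The concern does not hold as a reason to change the plan. It identifies a real but clerical looseness: one sentence about follow-up lacks a qualifier that its surroundings supply. Followed as a whole, the plan provides a post-removal assessment for 10 of 10 subjects, whatever their response to stimulation. The figure of 0 of 10 arises only if the sentence is separated from the bullet that follows it. No loss of data is shown, and the documents offer no basis for sizing a bias.

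The conclusion rests on two assumptions: that the team treats the one-month contact and TAPES as the commitments they are worded to be, and that a subject with replaced leads is assessed under the instruction to repeat testing. Both are the natural reading. The consequence is further limited because Aim 2 is a secondary, descriptive aim of a pilot whose Power Analysis section makes no power calculation, so no test or decision rule depends on the point.
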